#### 8.1.3.6 Overall survival

#### 8.2 Sample Size/Accrual Rate

#### 8.2.1 Sample Size

The sample size calculations address the specific primary hypothesis that patients treated with hippocampal-sparing PCI for SCLC will not experience as much decline in neurocognitive function as reported for the historical control of RTOG 0212 receiving the same dose of conventional PCI. The clinically meaningful difference and associated standard deviation are based on the RTOG study and the work of Meyers et al. The latter reported a mean score in the HVLT-R delayed recall change in patients treated only with whole-brain radiation therapy of 0.87 (from 7.04 at baseline to 6.17 at 6 months), with a standard deviation of 3.19. In RTOG 0212, the average decline in HVLT memory at six months is 1.13 (sd=2.80). We expect patients receiving hippocampal-sparing PCI to experience a smaller decline in cognitive function from baseline to six months, compared to the historical control group. The

onesided statistical hypothesis test is as follows: H0:  $\Delta \mu = 1$  vs. HA:  $\Delta \mu < 1$ , where  $\Delta \mu$  is the mean change in HVLT scores from baseline to 6 months for patients receiving hippocampal-sparing PCI (baseline minus 6-month score). With change measured in 100 patients, we will have 90% power to detect a meaningful change (0.88 points less change in HVLT scores over 6 months, i.e., mean change of 0.12) in our treated group with a one-sided test at the 5% level of significance, assuming a standard deviation of around 3. Similarly, we will have 80% power with a one-sided 5% level test to detect a mean change of 0.75 (with standard deviation equal to 3). We will enroll 125 patients to allow for up to 20% of patients to be not evaluable at 6 months.

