#### 8.4 Statistical Methods of Analysis

The primary objective of this study is to evaluate change in cognitive function as measured by the HVLT-R-delayed recall. We will compare hippocampal-sparing PCI to the historical experience of patients who received standard PCI in RTOG 0212. Each patient will be assessed pre-therapy and post-therapy, with the change at 6 months being the primary endpoint. Patient scores on the HVLT-R delayed recall section are whole numbers, ranging from 0 to 12, with lower scores indicating declining cognitive function. The score itself refers to the number of words a patient can recall from a list of 12 words. Therefore, if a patient initially is able to recall 8 words pre-therapy and is, at 6 months, able to only recall 6 words, their change in score would be 2. The primary endpoint (change score) is the difference between the pre-therapy and post-therapy scores. A change score of zero indicates preserved cognitive function. Change scores from -1 to -12 indicated improved cognitive function and are not expected. Summary statistics of the change scores, such as means, medians, standard deviations, and ranges will be listed separately by treatment (sparing PCI and historical standard PCI groups). We hypothesize that change scores from pre-therapy to 6 months post-therapy is lower among patients receiving hippocampal-sparing PCI compared to the historical PCI group in the RTOG study. We will use the Wilcoxon Signed-Rank test to test the change in HVLT-R scores over six months, relative to the expectation based on the historical information, according to the statistical hypotheses given in the sample size section (Section 8.2.1).

The analysis of the secondary outcome of HVLT-R-delay score change at 12 months will be performed as described above for the primary outcome. In addition, we will examine if there appears to be a trend to increasing change score over time for the treatment groups.

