#### 8.5 Safety Monitoring

We have included a formal statistical stopping rule for monitoring the occurrence of brain metastases. The article describing RTOG 0212 reported that the raw proportion of patients with brain metastases is 22% (29/131) at 1 year for the group getting 2.5 Gy in 10 fractions. We established a monitoring rule that will recommend considering stopping the study if there appears to be high probability that the risk of brain metastasis at 1 year is above 22%. Specifically, if the posterior probability that the risk exceeds 25% of brain metastasis by 1 year after treatment is 75% or greater (3:1 odds), then we will consider stopping the study. In this calculation, the number of patients with brain metastasis at 1 year is a binomial random variable. The prior

distribution for the risk of brain metastasis by 1 year is beta with parameters 29 & 102. Although we can apply the stopping rule calculation after every patient, we may monitor in batches of 10. The stopping rule is illustrated in the figure below.

Safety Monitoring Boundary

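### The 5% level and 90% power hold for a test against a fixed decline of 1 point, but do not carry over to the promised comparison with RTOG 0212, whose own sampling error is left out

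*Combined protocol and SAP*

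**What the plan says.** Section 1.1 states the primary objective relative to a historical control, and section 8.1.1 identifies that control as the RTOG 0212 arm given 25 Gy in 10 fractions. Section 8.4 puts it as a comparison: "We will compare hippocampal-sparing PCI to the historical experience of patients who received standard PCI in RTOG 0212".

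Section 8.2.1 draws on two historical sources. For RTOG 0212: "In RTOG 0212, the average decline in HVLT memory at six months is 1.13 (sd=2.80". For patients given whole-brain radiotherapy alone in a second study, it cites a mean change "of 0.87 (from 7.04 at baseline to 6.17 at 6 months), with a standard deviation of 3.19". Neither figure comes with a number of patients or a standard error.

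The hypothesis in 8.2.1 is one-sample and one-sided: mean decline with hippocampal sparing equal to 1 under the null, below 1 under the alternative. The sample size follows: "With change measured in 100 patients, we will have 90% power to detect a meaningful change". The difference that the authors have in mind is "0.88 points less change in HVLT scores over 6 months, i.e., mean change of 0.12". The level is 5%, one-sided, and the calculation is made "assuming a standard deviation of around 3". Section 8.4 tests this with a Wilcoxon signed-rank test against the historical expectation. It also lists descriptive statistics for the sparing and historical groups separately, but plans no estimate or interval for their difference.

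The only denominator given for the 25 Gy arm is in section 8.5, for a different outcome: "the raw proportion of patients with brain metastases is 22% (29/131) at 1 year".

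**The concern.** The question is posed about two groups of patients and answered with a test that treats one of them as a known constant. A significant result shows that mean decline in the new patients is below 1 point. It does not show, at the same error rate, that they declined less than patients like those in RTOG 0212, because the RTOG 0212 mean could be off by an amount similar to the new trial's own standard error.

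With no randomised control, this contrast is the trial's main message. With descriptive statistics for the two groups side by side and a p-value from the benchmark test, a reader will naturally attach that p-value to the difference between groups. The plan gives nothing that describes the uncertainty of that difference.

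The plan handles the same arm differently elsewhere. In section 8.5 its metastasis count enters as a beta(29, 102) prior, which gives the historical data finite weight. The primary endpoint has no counterpart.

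**Working it through.** **Inputs.** From 8.2.1: null value 1; alternative 0.12; treated SD 3; 100 evaluable patients; one-sided 5%; RTOG 0212 mean 1.13 and SD 2.80; second source 0.87. From 8.5: 131 patients in the 25 Gy arm's metastasis count. Not in the documents: m, the number of RTOG 0212 patients with a 6-month HVLT change. I assume m from 131 down to 40. The lower end is a choice made for illustration. Normal approximations are used throughout.

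**Step 1: reproduce the plan's figure.** The standard error of the treated mean is 3/√100 = 0.30. Power = Φ(0.88/0.30 − 1.645) = 90.1%; noncentral t gives 89.8%, and a signed-rank test with efficiency 3/π gives 88.9%. The required number is (3 × (1.645 + 1.282)/0.88)² = 99.5, so 100, and 100/0.8 = 125. The plan's arithmetic is sound for a fixed null of 1.

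**Step 2: what the planned rule does.** It rejects when the observed mean decline falls below about 1 − 1.645 × 0.30 = 0.507.

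**Step 3: add the control's sampling error.** SE of the difference = √(9/100 + 2.80²/m).

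- Control share of the variance = (2.80²/m) / SE².
- Power of a true one-sided 5% comparison of 0.12 with 1.13 = Φ(1.01/SE − 1.645).
- Error of the planned rule for a claim of less decline than RTOG 0212 = Φ((0.507 − 1.13)/SE). This is the chance of rejecting when sparing has no benefit, averaged over a true control mean distributed around 1.13 with standard error 2.80/√m.

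| m | Control SE | SE of difference | Control share | Power | Error |
|---|---|---|---|---|---|
| 131 | 0.245 | 0.387 | 40% | 83% | 5.4% |
| 100 | 0.280 | 0.410 | 47% | 79% | 6.4% |
| 75 | 0.323 | 0.441 | 54% | 74% | 7.9% |
| 60 | 0.361 | 0.470 | 59% | 69% | 9.2% |
| 40 | 0.443 | 0.535 | 69% | 60% | 12% |

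**Step 4: a check that does not need m.** If the true decline without sparing were the 0.87 of the second cited source, a treatment with no benefit would pass the test with probability Φ((0.507 − 0.87)/0.30) = 11%. That source is a different population, so this shows sensitivity to the benchmark; it does not estimate the RTOG 0212 mean.

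**The case against.** A fixed benchmark is an openly stated and common choice in a single-arm phase II trial. Section 8.2.1 defines its parameter as the mean change in the treated patients, and for that parameter 5% and 90% are correct. The null of 1 is also 0.13 below the RTOG 0212 mean. If the true control decline were exactly 1.13, a treatment with no benefit would pass only about 1.9% of the time (Φ((0.507 − 1.13)/0.30)). All of this stands, and it is why the benchmark test should stay. It does not supply an error rate when the control mean is uncertain, and it does not restore the power of the comparison.

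The range also rests on an unstated m. The sentence giving 1.13 names no arm, and 131 is a metastasis denominator. If 1.13 pools arms, m could exceed 131; at an illustrative m = 200 the same formulas give 4.1% error and 88% power. This too stands, and it is a reason to state m.

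Section 8.4 does include a general sentence about comparing patients with historical controls by suitable tests. It follows the Reliable Change Index paragraph, names no method, and does not fill the gap for the primary endpoint.

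Three stronger readings might be inferred, and the documents support none of them:

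- That a planned confidence interval is too narrow. None is planned for this endpoint; the only one in 8.4 is for median survival.
- That the tested constant is the RTOG 0212 mean. It is 1, not 1.13.
- That the error rate is 10% to 18% over this range of m. This requires 1 to be the RTOG 0212 estimate, whereas 8.2.1 reports 1.13.

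**Conclusion.** The concern holds as a mismatch between claim and inference; the plan's arithmetic is not at fault. The stated 5% and 90% apply to mean decline below 1 and to nothing wider. For a statement about RTOG 0212, with control SD 2.80 and m between 131 and 40, power is about 83% to 60%, and the planned rule's one-sided error is about 5.4% to 12%.

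The loss of power is present across that whole range. The inflation of the error rate is slight at m = 131, where the 0.13 margin absorbs most of it, and becomes material only if m is well below that. Similarly, the omitted share of the variance is 40% at m = 131 and passes one half only at smaller m. How serious the problem is cannot be settled until the number behind 1.13 is known.

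**What to change.** 1. Keep the one-sample test against 1 as the primary test, with the sample size unchanged.
2. State in 8.2.1 that the 5% level and 90% power apply to a fixed benchmark of 1.
3. State in 8.2.1 which RTOG 0212 arm, which HVLT measure and how many patients with a 6-month change lie behind 1.13. The text there refers only to HVLT memory, while the endpoint is delayed recall.
4. Add to 8.4 a two-sample (Welch) estimate of the difference in mean 6-month change from that arm, using its mean, SD and m. Report it with a 95% confidence interval beside any statement about RTOG 0212.

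The cost is a few lines of text and one historical number that must be obtained; no patients are added. The precision shown becomes less favourable: the half-width is 1.96 × 0.387 = 0.76 points at m = 131 and 1.96 × 0.535 = 1.05 at m = 40. The interval may therefore include zero when the primary test is significant. At m = 131 it excludes zero only if observed decline is below 1.13 − 0.76 = 0.37, while the primary test needs only 0.51. If the true decline is 0.12, the chance of excluding zero is Φ(1.01/SE − 1.96), about 74% at m = 131 and 47% at m = 40. For that reason the interval should accompany the claim and not be made the sole condition for it.

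### Section 8.2.1 claims 80% power at a mean change of 0.75; against the null of 1 that power is about 21%, and 80% belongs to a mean change of 0.25

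*Combined protocol and SAP*

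**What the plan says.** Section 8.2.1 (Sample Size) sets a one-sided test of H0: Δμ = 1 against HA: Δμ < 1. It defines Δμ by saying that it "is the mean change in HVLT scores from baseline to 6 months for patients receiving hippocampal-sparing PCI (baseline minus 6-month score"). A larger Δμ therefore means more decline.

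Two power statements follow, both for a one-sided 5% test.

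- The first reads: "With change measured in 100 patients, we will have 90% power to detect a meaningful change". The effect is given in two forms, "0.88 points less change in HVLT scores over 6 months, i.e., mean change of 0.12", "assuming a standard deviation of around 3".
- The second is introduced as similar to the first: "we will have 80% power with a one-sided 5% level test to detect a mean change of 0.75", "with standard deviation equal to 3".

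The enrolment target comes next: "We will enroll 125 patients to allow for up to 20% of patients to be not evaluable at 6 months".

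Section 8.4 names the Wilcoxon signed-rank test for the primary comparison.

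**The concern.** The first power statement keeps two quantities apart: the value of Δμ under the alternative (0.12) and its distance from the null (1 − 0.12 = 0.88). The second gives only one number, 0.75, and calls it a mean change. In the section's own terms the alternative is then Δμ = 0.75, at a distance of 0.25 from the null.

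The two statements cannot both hold. Sample size, SD and significance level are the same, yet the effect falls from 0.88 to 0.25 while the power falls only from 90% to 80%.

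What is at stake is how the result is read. These are the only two power statements for the primary endpoint. Anyone relying on the second could take a non-significant result as evidence against a decline of 0.75 rather than 1, when the trial had about a 1-in-5 chance of detecting that difference.

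**Working it through.** **Inputs, all from Section 8.2.1 unless noted**

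- Null value of Δμ: 1, alternative below 1
- Evaluable patients: n = 100
- SD of the change score: 3
- One-sided α = 0.05, so z = 1.645
- Standard error: 3/√100 = 0.30

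**Formula.** For a one-sample test of a mean, power = Φ(d/SE − 1.645), where d = 1 − Δμ under the alternative.

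**Step 1: reproduce the 90% statement.** Δμ = 0.12, d = 0.88. Power = Φ(0.88/0.30 − 1.645) = Φ(1.288) = 90.1%, or 89.8% with the noncentral t. The required n is 100. This agrees with the plan and confirms the method.

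**Step 2: the 80% statement as printed.** Δμ = 0.75, d = 0.25. Power = Φ(0.25/0.30 − 1.645) = Φ(−0.812) = 20.9%, or 20.7% with the noncentral t. This does not agree.

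**Step 3: read 0.75 as the difference.** d = 0.75, Δμ = 0.25. Power = Φ(0.75/0.30 − 1.645) = Φ(0.855) = 80.4%, or 79.9% with the noncentral t. This agrees. Working backwards, the difference detectable with 80% power is 0.30 × (1.645 + 0.842) = 0.746, which rounds to the printed 0.75.

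**Step 4: a check without a power formula.** The z-test rejects only when the observed mean change is below 1 − 1.645 × 0.30 = 0.51. An observed mean of exactly 0.75 gives z = 0.25/0.30 = 0.83 and a one-sided p of about 0.20. Power at a true value that would not itself be significant if observed must be below 50%.

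**Step 5: can another input rescue the printed sentence?** The alternative is held at Δμ = 0.75 and one item is changed at a time, except in the row that changes two.

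| Change | Power |
|---|---|
| SD 2.80 (RTOG 0212 figure) | 22.6% |
| SD 3.19 (the other source SD) | 19.5% |
| n = 125 | 23.8% |
| Two-sided 5% | 13.0% |
| Null 1.13 | 35.3% |
| Null 1.13 and SD 2.80 | 38.7% |
| Null 0.87 | 10.7% |

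None comes near 80%. Reaching it at Δμ = 0.75 would take an SD of about 1.0, or (2.487 × 3/0.25)² ≈ 890 evaluable patients (891 when rounded up). That number shows the size of the mismatch and is not a suggested sample size.

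**Step 6: the planned test.** A simulation of the one-sided signed-rank test (4,000 runs, normal data, SD 3, n = 100) gave power of 21.6% at Δμ = 0.75, 77.4% at Δμ = 0.25 and 88.5% at Δμ = 0.12. The choice of test does not explain the discrepancy.

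**Step 7: enrolment.** 100/(1 − 0.20) = 125, as stated.

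**The case against.** The best defence is that the power calculation is sound and only a label is wrong. The sentence is tied to the one before it, where the effect first appears as a difference. Going from 90% to 80% power with everything else fixed moves the detectable difference from 0.88 to about 0.75, which is the number printed. Nothing else in the plan uses 0.75: the sample size rests on the 90% statement, and the hypotheses, significance level, primary test and brain-metastasis stopping rule do not depend on it. A careful reader would also notice that the adjacent sentences conflict.

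Most of this stands. It is very probably a labelling slip, and the 21% must not be quoted as the trial's power for its main design alternative. It does not rescue the sentence, because the section defines the mean change explicitly and uses the term in that sense one sentence earlier. No other passage corrects it. The claim that readers would be misled is too strong; that they could be is fair.

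A second point also stands. The 80% is a normal or t approximation, and the signed-rank test gives about 77% at a mean change of 0.25 under normal data. The corrected wording should name its basis.

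**Conclusion.** The printed statement is wrong. With a null of 1, SD 3, 100 evaluable patients and a one-sided 5% test, power at a mean change of 0.75 is about 21%, roughly 59 percentage points below the stated 80%. The stated power belongs to a mean change of 0.25. In terms of the null decline, the trial can reliably detect a reduction from 1.00 to 0.25, not from 1.00 to 0.75.

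The conclusion rests on the section's own definition of the mean change and on its SD. It does not depend on choosing between the z, t and signed-rank tests, or between the two source SDs. The error overstates sensitivity to a small benefit but does not drive the design, so its severity is modest.

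**What to change.** Reword the second power statement in Section 8.2.1 so that it gives both quantities, as the first does: 80% power, one-sided 5% level, for 0.75 points less decline than the null, meaning a true mean change of 0.25, with SD 3 and 100 evaluable patients. Add that the figure is a normal or t approximation and that the signed-rank test planned in Section 8.4 would have slightly lower power (about 77% under normal data).

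If a true mean change of 0.75 really is an effect of interest, state that the power for it is about 21%.

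The cost is one sentence of protocol text and a less favourable detectable effect on paper. No change to the sample size, hypotheses or analysis is needed.

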#### 8.2.2 Accrual

We anticipate enrollment of approximately 2 patients per month to the protocol with accrual completed in approximately 5 years.

#### 8.3 Stratification Factors

There will be no stratification factors upon initial enrollment in the protocol.

#### 8.4 Statistical Methods of Analysis

The primary objective of this study is to evaluate change in cognitive function as measured by the HVLT-R-delayed recall. We will compare hippocampal-sparing PCI to the historical experience of patients who received standard PCI in RTOG 0212. Each patient will be assessed pre-therapy and post-therapy, with the change at 6 months being the primary endpoint. Patient scores on the HVLT-R delayed recall section are whole numbers, ranging from 0 to 12, with lower scores indicating declining cognitive function. The score itself refers to the number of words a patient can recall from a list of 12 words. Therefore, if a patient initially is able to recall 8 words pre-therapy and is, at 6 months, able to only recall 6 words, their change in score would be 2. The primary endpoint (change score) is the difference between the pre-therapy and post-therapy scores. A change score of zero indicates preserved cognitive function. Change scores from -1 to -12 indicated improved cognitive function and are not expected. Summary statistics of the change scores, such as means, medians, standard deviations, and ranges will be listed separately by treatment (sparing PCI and historical standard PCI groups). We hypothesize that change scores from pre-therapy to 6 months post-therapy is lower among patients receiving hippocampal-sparing PCI compared to the historical PCI group in the RTOG study. We will use the Wilcoxon Signed-Rank test to test the change in HVLT-R scores over six months, relative to the expectation based on the historical information, according to the statistical hypotheses given in the sample size section (Section 8.2.1).

The analysis of the secondary outcome of HVLT-R-delay score change at 12 months will be performed as described above for the primary outcome. In addition, we will examine if there appears to be a trend to increasing change score over time for the treatment groups.

The Reliable Change Index will measure meaningful change between baseline and 6 and 12 months for HVLT–R, Trail Making Test part A and B, COWAT. The Reliable Change Index is derived from the standard error of measurement (SEM) for each test in the battery. The SEM is calculated from the test–retest reliability (r) and the standard deviation of test scores (SD): SEM=sqrt[SD×(1-r)]. The standard error of the difference (SEdiff) is then calculated as SEdiff =sqrt[ $2\times(SEM)^2$ ]. For each test in the neurocognitve battery, the Reliable Change Index value will be determined *a priori* for that particular test to determine whether a change from baseline is clinically meaningful.

We will compute summary statistics and compare our patients to the historical controls based on tests that are appropriate for the type of data.

[figure not shown]
Quality of Life on our study will be assessed using EORTC Quality of Life questionnaire (QLQ-C30) and the Brain Cancer Module 20 (BN 20) pre-therapy, at 6 months, and at 12 months after therapy. For each module, summary statistics of the scores will be reported for each study time point. Change scores in quality of life from pre-therapy to post-therapy will be calculated and tested via paired t-tests for the hippocampal-sparing PCI treatment group. We may fit mixed-effect models to explore changes in quality of life assessments over time.

We will tabulate development of brain metastases within 0.5 mm of the hippocampus. We will report adverse events based on CTCAE v4.0 by frequency tables. We will test the proportion of patients who develop brain metastases via binomial test. Overall survival will be measured from the start of treatment to death or last followup. For subjects who alive or lost follow up at the end of study, overall survival will be censored at the last follow up date. Overall survival probabilities will be estimated via the Kaplan-Meier method; median survival and 95% confidence interval via Greenwood's formula for variance will be reported.

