#### **1.2** Secondary Objectives

- 1.2.1 Evaluate performance on HVLT-R delayed recall at 12 months following hippocampal-sparing PCI relative to historical control receiving standard PCI.
- 1.2.2 Evaluate composite cognitive function at 6 and 12 months following hippocampal-sparing PCI relative to a historical control receiving standard PCI
- 1.2.3 Evaluate quality of life following hippocampal-sparing PCI relative to a historical control receiving standard PCI.
- 1.2.4 Determine whether development of brain metastases following hippocampalsparing PCI is higher than expected.
- 1.2.5 Determine whether development of leptomeningeal carcinomatosis following hippocampal sparing PCI is higher than expected
- 1.2.6 Evaluate overall survival following hippocampal sparing PCI.

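### The 12-month memory test has no 12-month historical reference: the only null it can inherit is the 6-month decline of 1

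*Combined protocol and SAP*

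**What the plan says.** Section 1.2 lists as objective 1.2.1: "Evaluate performance on HVLT-R delayed recall at 12 months following hippocampal-sparing PCI relative to historical control receiving standard PCI". The comparison is therefore with the control, at 12 months.

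Section 8.4 gives the formal method for it in one sentence: "The analysis of the secondary outcome of HVLT-R-delay score change at 12 months will be performed as described above for the primary outcome". The primary analysis in the same section is a Wilcoxon signed-rank test of the change score, "relative to the expectation based on the historical information, according to the statistical hypotheses given in the sample size section (Section 8.2.1").

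Section 8.2.1 contains one pair of hypotheses, a mean decline of 1 against a mean decline below 1. The parameter "is the mean change in HVLT scores from baseline to 6 months for patients receiving hippocampal-sparing PCI (baseline minus 6-month score"). Two historical figures stand behind it, and both are 6-month declines:

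- For patients given whole-brain radiation alone: "0.87 (from 7.04 at baseline to 6.17 at 6 months), with a standard deviation of 3.19".
- For the trial named as the historical control: "In RTOG 0212, the average decline in HVLT memory at six months is 1.13 (sd=2.80").

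Section 8.4 also plans summaries of the change scores for the sparing and historical groups, and adds that "we will examine if there appears to be a trend to increasing change score over time for the treatment groups". It further plans a Reliable Change Index for HVLT-R at 6 and 12 months, followed by a general statement that the trial's patients will be compared with historical controls.

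**The concern.** The control in this single-arm trial enters the formal test only as a constant. If that constant belongs to a different time point from the outcome, the test does not address the stated objective. Following the cross-references from Section 8.4 to Section 8.2.1, the only constant available for the 12-month test is 1, and it is defined for the first 6 months.

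The error could run either way. If patients given standard PCI have declined by less than 1 point at 12 months, an ineffective technique would be declared better too often. If they have declined by more than 1 point, a real benefit would often be missed. Nor does the plan commit itself to a decline that stays constant after 6 months, since it sets out to look for a trend over time.

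**Working it through.** **Inputs from Section 8.2.1 (all for 6 months).** Null decline 1; benefit 0.88 points (mean change 0.12); SD about 3; one-sided 5%; 100 evaluable patients; 125 enrolled, allowing up to 20% not evaluable.

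**Inputs not in the documents.** The control's mean decline at 12 months, written D; the SD at 12 months; the number tested at 12 months. I assume SD 3 and n = 80, show n = 60 and 100 as a range, and vary D.

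**Step 1: reproduce the 6-month design (normal approximation).**

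- n = [SD × (z₀.₉₅ + z₀.₉₀) / 0.88]² = [3 × (1.645 + 1.282) / 0.88]² = 99.5, rounded up to 100.
- Power at n = 100: Φ(0.88 / (3/√100) − 1.645) = Φ(1.288) = 90.1%.
- Enrolment: 100 / (1 − 0.20) = 125.

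The plan's figures reproduce. A simulated signed-rank test on scores rounded to whole numbers gives about 88% power at n = 100.

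**Step 2: trace the 12-month null.** Objective 1.2.1 leads to the single sentence in Section 8.4, then to the primary test, then to the Section 8.2.1 hypotheses. Only one pair is found there. Its value, 1, equals the average of the two quoted declines, (0.87 + 1.13)/2 = 1.00, and both are 6-month figures. No 12-month mean, SD or null value appears anywhere.

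**Step 3: behaviour of a 12-month test against 1.** The chance of rejecting is Φ((1 − m) / (3/√n) − 1.645), where m is the true mean decline in the trial's patients. At n = 80, 3/√80 = 0.335.

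No true benefit (m = D); the nominal rate is 5%:

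| Control decline at 12 months, D | n = 80 | n = 60 to 100 |
|---|---|---|
| 0.5 | Φ(0.5/0.335 − 1.645) = 44% | 36% to 51% |
| 0.75 | Φ(0.25/0.335 − 1.645) = 18% | 16% to 21% |
| 0.87 | Φ(0.13/0.335 − 1.645) = 10% | 10% to 11% |
| 1 | 5% | 5% |
| 1.13 | 2% | 2% |

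True benefit of 0.88 points (m = D − 0.88):

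| D | m | n = 80 | n = 60 to 100 |
|---|---|---|---|
| 1 | 0.12 | Φ(0.88/0.335 − 1.645) = 84% | 73.5% to 90% |
| 1.13 | 0.25 | Φ(0.75/0.335 − 1.645) = 72% | 61.5% to 80% |
| 1.25 | 0.37 | Φ(0.63/0.335 − 1.645) = 59% | 49% to 68% |
| 1.5 | 0.62 | Φ(0.38/0.335 − 1.645) = 30% | 25% to 35% |

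A null set equal to D would hold the false-positive rate at 5% and the power at 84% for n = 80, whatever D is.

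**Step 4: check the approximation.** The simulated signed-rank test at n = 100 with no benefit rejects 50% of the time at D = 0.5 (formula: 51%) and 5% at D = 1.

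**The case against.** The strongest reply is that no sentence in the plan sets the 12-month null at 1. Section 8.2.1 ties its parameter to the first 6 months, so it cannot be carried to 12 months without substituting something. The sentence in Section 8.4 may mean the same method against a 12-month historical expectation that was left unstated. That is a fair reading, and it stands as a limit on the point. It does not remove the problem, because the null would then be unspecified and could be chosen after the data are seen.

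A reader might also infer that the trial will be unable to say anything about 12-month memory relative to the control. The documents do not support that. The historical-group summaries, the trend by treatment group and the 12-month Reliable Change Index leave room for a descriptive comparison, provided 12-month control data are obtained.

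Nor do the documents show that the control's 12-month decline differs from 1, or in which direction. Planning to look for a trend is not evidence of one. Patients in the historical cohort also had to be alive to be tested at 12 months, so survival alone does not show that the benchmark moves.

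Finally, the largest error rates come from the ends of an assumed range. At the documents' own declines of 0.87 and 1.13, which are 6-month values, the effect is milder: about 10% false positives and about 72% power. The endpoint is secondary, and the primary 6-month test and the sample size are untouched.

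**Conclusion.** The point holds in a limited form. Followed as written, Section 8.4 gives the 12-month test a 6-month benchmark, and that test is valid for objective 1.2.1 only if the control's 12-month decline happens also to be 1. Read generously, the 12-month null is missing. Both readings call for the same correction.

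No single corrected figure can be given, because the 12-month control decline is not in the documents. With SD 3, n = 80 and a one-sided 5% test, all assumed for 12 months, assumed control declines from 0.5 to 0.87 give false-positive rates from 44% down to 10%. Assumed declines from 1.13 to 1.5 give power from 72% down to 30%, against 84% with a matching null. If the control decline is exactly 1, there is no distortion. These figures show how sensitive the test is to the missing value; they do not predict how far off it will be.

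**What to change.** In Section 8.4, replace the reference back to the primary analysis with a 12-month null and alternative of its own. Set the null equal to the mean decline from baseline to 12 months in the RTOG 0212 25 Gy arm, state that value with its source, and fix it before the 12-month data are analysed.

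If no such value can be obtained, report the 12-month mean change with a confidence interval and label the comparison in objective 1.2.1 as descriptive.

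The cost is a change of wording in Section 8.4 and, in the second case, in objective 1.2.1. No extra patients, visits or tests are needed. The downside is that the 12-month result may become descriptive.
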